5.1.3 AE and Concomitant medication date imputation

Missing or incomplete dates will be listed as it is in any listings.

Incomplete start date of an adverse event or concomitant medication taken will be handled by following rule:

	Missing	Imputation	Exception
Start date (AE, concomitant medication)	Day	01	Default to Study Day 1 if an adverse event starts the same year and month as Study Day 1 and the flag indicates that the adverse event started on or after the first dose on the Adverse Events eCRF
	Day/Month	01Jan	Default to Study Day 1 if an event started the same year as Study Day 1 and the flag indicates that the adverse event started on or after the first dose on the Adverse Events eCRF
	Day/Month/Year	No imputation	

5.1.4 Prior therapies date imputation

For prior medications with a stop date prior to the treatment phase (not possible to be at or after first drug administration), the start date will be imputed as the earliest possible start date and the stop date as the latest possible stop date:

For a missing/incomplete start date the minimum of the following will be imputed:

- The maximum of the earliest possible start date and the imputed birth date;
- The latest possible start date;
- The latest possible stop date.

For a missing/incomplete stop date the maximum of the following will be imputed:

- The minimum of the latest possible stop date and the date of first drug administration -1;
- The earliest possible stop date;
- The earliest possible start date.

Here, the earliest (latest) possible date is defined as:

- The date itself if it is complete;
- The date of the first (last) day of the month, if month and year are available but day is missing;
- The date of the first (last) day of the year, if year is available but day and month are missing;

- A very early (late) date, e.g., 01JAN1000 00:00hrs (01JAN3000 23:59hrs), if the date is completely missing.

5.1.5 Missing Baseline Evaluation

Missing baseline evaluations will not be imputed.

All subjects included in the full analysis set will have baseline monthly rate or monthly average of migraine and non-migraine headaches related measurements after applying proration rule defined in [Section 5.1.2](#) since only subject with $\geq 80\%$ compliance of eDiary use during baseline will be eligible for randomization.

5.1.6 Missing Post-baseline Evaluation in Double-Blind Treatment Epoch

Primary analysis of continuous efficacy endpoints during the 12-week randomized DBTE will be conducted using the generalized linear mixed model on observed data without imputation. In the sensitivity analysis on primary and secondary efficacy endpoints during the 12-week DBTE, missing continuous efficacy endpoints will be handled using baseline observation carried forward (BOCF) method, and multiple imputation (MI) with assumption of missing at random (MAR) and missing not at random (MNAR) (with control-based pattern imputation and treatment effect adjusted imputation), respectively.

In BOCF method, post-baseline missing continuous efficacy endpoints during double-blind treatment phase will be imputed using the baseline observed value. For example, if subject has all of the post-baseline values as missing, then all of the post-baseline values will be imputed using the observed baseline value.

In non-responder imputation (NRI) method, post-baseline missing dichotomous secondary efficacy endpoint (responder [Yes/No] based on $\geq 50\%$ reduction from baseline in monthly migraine days) during double-blind treatment phase will be imputed as non-responder at each corresponding time point.

If the proportion of missing data in primary endpoint is high (eg, $> 20\%$ for primary analysis at week 12), further analysis will be performed to

- examine the frequency and reason of missing data
- determine if there are any patterns in the missing data
- distinguish true missing values from other unknown values (eg, due to measurement or sample processing error)

5.2 AEs coding/grading

Adverse events are coded using the Medical dictionary for regulatory activities (MedDRA) terminology.

Adverse event severity is graded based on NCI Common Toxicity Criteria version 4 or higher, which is available at the following: http://evs.nci.nih.gov/ftp1/CTCAE/CTCAE_4.03_2010-06-14_QuickReference_5x7.pdf

The CTCAE displays Grades 1 through 4 with unique clinical descriptions of severity for each AE based on this general guideline:

Grade 1 - Mild; asymptomatic or mild symptoms; clinical or diagnostic observations only; intervention not indicated.

Grade 2 - Moderate; minimal, local or noninvasive intervention indicated;

Grade 3 - Severe or medically significant but not immediately life-threatening; hospitalization or prolongation of hospitalization indicated; disabling;

Grade 4 - Life-threatening consequences; urgent intervention indicated.

The mapping to Grade 3 and 4 will be done manually, in a case by case basis.

For those cases, the list of patients with severe (Yes) or serious AEs (Yes) with relevant information about hospitalization, its outcome and relation to treatment will be presented to study clinical team – discussion co-lead by Clinical Development Medical Director (CDMD) and Brand Safety Leader (BSL) - to define if the event may be mapped to grade 3 or grade 4. The decision about Grade 3 or 4 will be documented and saved as excel file in GPS CAMG334A2301 study folder and documented in CREDI.

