7.1 Adverse events

An adverse event (AE) is any untoward medical occurrence (e.g., any unfavorable and unintended sign [including abnormal laboratory findings], symptom or disease) in a patient or clinical investigation patient from randomization (Visit 101) until the end of study visit. Any events occurring during the Screening and Baseline Epochs should be documented as medical history. An AE may or may not be temporally or causally associated with the use of a medicinal (investigational) product.

In addition, all reports of intentional misuse and abuse of the product are also considered an adverse event irrespective if a clinical event has occurred.

The occurrence of adverse events must be sought by non-directive questioning of the patient at each visit during the study. Adverse events also may be detected when they are volunteered by the patient during or between visits or through physical examination findings, laboratory test findings, or other assessments.

Abnormal laboratory values or test results constitute adverse events only if they fulfill at least one of the following criteria:

- they induce clinical signs or symptoms,
- they are considered clinically significant,
- they require therapy.

Clinically significant abnormal laboratory values or test results must be identified through a review of values outside of normal ranges/clinically notable ranges, significant changes from baseline or the previous visit, or values which are considered to be non-typical in patient with underlying disease. Investigators have the responsibility for managing the safety of individual patient and identifying adverse events. Alert ranges for laboratory and other test abnormalities are included in [Appendix 1](#).

Adverse events must be recorded in the Adverse Events eCRF under the signs, symptoms or diagnosis associated with them, accompanied by the following information:

- the severity grade

- mild: usually transient in nature and generally not interfering with normal activities
- moderate: sufficiently discomforting to interfere with normal activities
- severe: prevents normal activities
- its relationship to the study treatment (no/yes)
- its duration (start and end dates) or if the event is ongoing an outcome of not recovered/not resolved must be reported
- whether it constitutes a serious adverse event (SAE - See [Section 7.2](#) for definition of SAE) and which seriousness criteria have been met
- action taken regarding [investigational] treatment.

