2.7.1 Adverse events (AEs)

The Medical Dictionary for Regulatory Activities (MedDRA) version 18.0 or later will be used to code all adverse events (AE) to a system organ class (SOC) and a preferred term (PT). All adverse events will be graded using the Common Terminology Criteria for Adverse Events (CTCAE) Version 4.03 (see details in [Section 5.2](#)). All adverse event tables will be summarized by treatment group.

AE tables by SOC and PT (and grade), will be sorted alphabetically by SOC and then descending order of frequency based on the AMG 334 140 mg dose by PT within each SOC. AE tables by preferred term only will be sorted in descending order of frequency based on the AMG 334 140 mg dose, then the placebo dose and then alphabetically.

Overall subject incidence of AEs will be summarized for all treatment-emergent AEs (TEAEs), serious AEs, AEs leading to withdrawal of IP, and fatal AEs for the DBTP.

Subject incidence of all TEAEs, serious AEs, AEs leading to withdrawal of IP, serious AEs leading to withdrawal of IP, fatal AEs will be tabulated by SOC and PT for the DBTE.

In addition, subject incidence of all treatment-emergent AEs and serious AEs will be tabulated by SOC, PT and CTCAE grade for the DBTE.

Subject incidence and exposure-adjusted subject incidence of all TEAEs and serious AEs will be tabulated by PT in descending order of frequency for the DBTE.

Treatment-related treatment-emergent AEs will be summarized for DBTE by SOC, PT and CTCAE grade.

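### Adverse event severity is tabulated only by CTCAE grade, with Grades 3 and 4 assigned case by case by the sponsor, so those rows may not reflect the severity that investigators recorded

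*SAP*

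**What the plan says.** Protocol 7.1 defines severity on three levels, by how far the event disturbs normal activities:

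- "mild: usually transient in nature and generally not interfering with normal activities"
- "moderate: sufficiently discomforting to interfere with normal activities"
- "severe: prevents normal activities"

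Relationship to study treatment (no/yes) is a separate item on the same form, and so is "whether it constitutes a serious adverse event". The section does not ask for a CTCAE grade.

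SAP 2.7.1 uses a different scale: "All adverse events will be graded using the Common Terminology Criteria for Adverse Events (CTCAE) Version 4.03". It then plans that "subject incidence of all treatment-emergent AEs and serious AEs will be tabulated by SOC, PT and CTCAE grade for the DBTE", and summarises treatment-related treatment-emergent events by grade as well. No table by the recorded mild, moderate or severe rating is planned.

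SAP 5.2 describes Grades 1 to 4, labelling Grade 1 as mild and Grade 2 as moderate. For the upper grades it says: "The mapping to Grade 3 and 4 will be done manually, in a case by case basis". The study clinical team, co-led by two sponsor roles, is shown "the list of patients with severe (Yes) or serious AEs (Yes) with relevant information about hospitalization, its outcome and relation to treatment" and decides whether an event may be placed in Grade 3 or 4. The decision is documented and filed.

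**The concern.** The collected scale and the analysed scale differ, and the step between them has no written rule at the top end. Severity, seriousness and causality are three attributes that the protocol records separately. The SAP brings all three into the grading step: severity or seriousness puts an event on the list, and causality is in view when the grade is chosen. The Grade 3 and 4 rows are what a safety reader looks at first. If those rows rest on unscripted sponsor judgement, and the investigator's rating appears in no severity table beside them, a reader cannot tell whether a Grade 3 entry means that the investigator called the event severe or that a milder event was serious.

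**Working it through.** No arithmetic applies, because the documents state no adverse event rate, grade count or grading algorithm. The check is to cross the three recorded severity levels with seriousness (3 × 2 = 6 types of event) and follow each through SAP 5.2.

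- **Mild or moderate, not serious (2 types).** These never reach the review list. By the SAP's own labels they fall in Grade 1 and Grade 2. Recorded severity is kept, although the mapping is implied by the labels and not stated.
- **Severe, serious or not (2 types).** These are on the list. Grade 3 is labelled severe and Grade 4 life-threatening, so one recorded level is divided into two grades by case review.
- **Mild or moderate, but serious (2 types).** These are also on the list. The SAP does not say what grade they receive if they are not moved up, or what would justify moving them.

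In the third group, seriousness alone can be enough to meet the Grade 3 description. SAP 5.2 places medically significant events, and events with hospital admission or a longer stay, in Grade 3. Protocol 7.2.1 uses both as criteria for a serious event. It also makes every malignant neoplasm serious on grounds of medical significance when no other criterion applies, whatever its severity. An event rated moderate that led to admission can therefore be tabulated as Grade 3 under the SAP's own text.

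Two consequences follow for the tables in SAP 2.7.1:

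- In all three by-grade tables, every entry in the Grade 3 and 4 rows has passed through the manual review, since no other route to those grades is described.
- In the serious-event table, every event is on the review list by definition, so grade there may partly restate seriousness.

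On causality, none of the grade descriptions in SAP 5.2 refers to relation to treatment, yet the reviewers see it, and the same grades feed the treatment-related table.

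On timing, Protocol 5.4 keeps sponsor personnel blinded until the double-blind epoch and primary analysis conclude, and Protocol 8.3 releases treatment codes after database lock. SAP 5.2 requires documentation but does not say that grading is complete before that point.

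**The case against.** The strongest case for the plan is that the review does a job the recorded scale cannot do. The recorded scale stops at severe, while Grade 4 means life-threatening, and in Protocol 7.2.1 that is a seriousness criterion. A rule from recorded severity alone cannot separate Grade 3 from Grade 4. Hospital admission and medical significance are in the SAP's Grade 3 text, so grading an admitted patient's event as 3 applies the stated scale and is not an error against it. All of this stands.

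A reader might infer more than the documents support in four ways:

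- **That all grades are set by hand.** Only Grades 3 and 4 are.
- **That a serious event must become Grade 3 or 4.** The list selects cases for review, and the wording is permissive. Serious is not equated with severe.
- **That a protocol-specified severity table has been lost.** Protocol 9.5.2 promises treatment-emergent incidence by system organ class and preferred term only.
- **That a particular number of patients would be upgraded.** The documents give neither the frequency of serious but non-severe events nor an expected Grade 3 or 4 count.

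The consequences are also limited. SAP 2.7 plans no between-arm test of safety. Serious events already have their own table by system organ class and preferred term. The overall counts of treatment-emergent, serious, withdrawal-related and fatal events do not depend on grade.

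The objection does not explain why the collected severity is tabulated nowhere, why causality is shown to the graders, or what happens to a serious event rated mild or moderate.

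**Conclusion.** The concern holds for the Grade 3 and 4 rows only. Those rows may not reflect recorded severity, because serious events rated mild or moderate may be moved into them and because the recorded level of severe is split without a written rule. Of the six types of event, two keep their recorded level, two are split by judgement and two may be moved. The number of patients affected cannot be derived from the documents. The effect is confined to descriptive safety tables, and bias between arms is limited provided that grading is done while the sponsor is blinded. The protocol supports that, but SAP 5.2 does not tie grading to it. The conclusion assumes that Grades 1 and 2 follow their mild and moderate labels, as the SAP implies. The change is worth making because the severity field is already collected.

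**What to change.** Make the investigator's recorded severity, taken as the maximum per patient, the basis of the severity tables for treatment-emergent, serious treatment-emergent and treatment-related treatment-emergent events.

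If CTCAE grades are kept as a supplement, amend SAP 5.2 to:

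- state that mild maps to Grade 1 and moderate to Grade 2;
- write the rule for severe events, where the life-threatening criterion may be used to separate Grade 4;
- write the rule for events that are serious but not severe;
- remove relation to treatment from the review list;
- require the grades to be locked before unblinding.

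The cost is SAP wording and a few extra descriptive tables. No new data are needed, and no efficacy analysis changes.

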5.3 Laboratory parameters derivations

CTCAE grading for the laboratory toxicity will not be derived.

5.4 Statistical models

5.4.1 Primary analysis

Primary Hypothesis

The null hypothesis stating that the odds ratio between the two treatment arms less than or equal to 1 will be tested against the one-sided alternative.

$$H_0: \theta_1 \leq 1 \text{ vs } H_1: \theta_1 > 1$$

where θ_1 is the odds ratio of active over corresponding placebo.

The primary analyses will compare the 50% response rate, which is defined as the proportion of patients who achieve at least a 50% reduction from baseline in monthly migraine days in the last month (month 3) of the Double-Blind Treatment Epoch, between AMG334 140 mg vs placebo.

Test statistic

After the missing data are imputed as non-response a Cochran-Mantel-Haenszel (CMH) test stratified by the migraine frequency (4-7 and 8-14 monthly migraine days strata) will be used under a significance level of 0.025, one-sided (0.05, two-sided) to evaluate the association between the 50% responder rate and the treatment. The estimated common odds ratio, 95% confidence intervals and two-sided p-values will be reported.

Additionally, the estimated common relative risk and risk difference with their asymptotic (Wald) confidence limits will be provided. They will be got using SAS, PROC FREQ with options CMH, RELRISK, RISKDIFF under TABLE statement.

Sensitivity analysis for primary endpoint

- (1) Without any imputation for missing data, adjusted odds ratios from a generalized linear mixed model that includes treatment group, baseline migraine days, stratification factor, scheduled visit, and the interaction of treatment and scheduled visit using observed data with type of unstructured covariance matrix (UN). Restricted maximum likelihood estimation will be used.
- (2) Logistic regression analysis will be used to test the superiority of AMG334 arm in the 50% response rate after the missing data are imputed as non-response. Baseline migraine days will be used as a covariate along with treatment and stratification factor as fixed effects in the model.
- (3) Stratified CMH test will be used to support the superiority of AMG334 arm in the 50% response rate after the missing data are imputed based on MAR and MNAR assumptions. The odds ratio of treatment group compared to placebo group with associated 95% confidence intervals and p-values will be provided.

5.4.2 Analysis methods

Generalized Linear Mixed Model

Generalized mixed effects repeated measure model fits data with correlations or nonconstant variability and where the response is not necessarily normally distributed, which is also known as generalized linear mixed models (GLMM). The correlations can arise from repeated observation of the same sampling units, shared random effects in an experimental design, spatial (temporal) proximity, multivariate observations, and so on.

GLMMs, like linear mixed models, assume normal (Gaussian) random effects. Conditional on these random effects, data can have any distribution in the exponential family. The exponential family comprises many of the elementary discrete and continuous distributions. The binary, binomial, Poisson, and negative binomial distributions, for example, are discrete members of this family. The normal, beta, gamma, and chi-square distributions are representatives of the continuous distributions in this family.

Suppose Y represents the $(n \times 1)$ vector of observed data and γ is a $(r \times 1)$ vector of random effects. GLMM Models assume that

$$E(Y | \gamma) = g^{-1}(X\beta + Z\gamma)$$

where g is a differentiable monotonic link function and $1/g$ is its inverse. The matrix X is an $(n \times p)$ matrix of rank k , and Z is an $(n \times r)$ design matrix for the random effects. The random effects are assumed to be normally distributed with mean 0 and variance matrix G .

The GLMM contains a linear mixed model inside the inverse link function. This model component is referred to as the linear predictor,

$$\eta = (X\beta + Z\gamma)$$

The variance of the observations, conditional on the random effects, is

$$\text{Var}[Y | \gamma] = A^{1/2} R A^{1/2}$$

The matrix A is a diagonal matrix and contains the variance functions of the model. The variance function expresses the variance of a response as a function of the mean.

The GLIMMIX procedure distinguishes two types of random effects. Depending on whether the parameters of the covariance structure for random components in your model are contained in G or in R , the procedure distinguishes between “G-side” and “R-side” random effects. The associated covariance structures of G and R are similarly termed the G-side and

R-side covariance structure, respectively. R-side effects are also called “residual” effects. Simply put, if a random effect is an element of Σ , it is a G-side effect and you are modeling the G-side covariance structure; otherwise, you are modeling the R-side covariance structure of the model. Models without G-side effects are also known as marginal (or population-averaged) models. Models fit with the GLIMMIX procedure can have none, one, or more of each type of effect.

For a model containing random effects, the GLIMMIX procedure, by default, estimates the parameters by applying pseudo-likelihood techniques as in [Wolfinger and O’Connell 1993](#) and [Breslow and Clayton 1993](#). You can also fit generalized linear mixed models by maximum likelihood where the marginal distribution is numerically approximated by the Laplace method (METHOD=LAPLACE) or by adaptive Gaussian quadrature (METHOD=QUAD).

Once the parameters have been estimated, you can perform statistical inferences for the fixed effects and covariance parameters of the model. Tests of hypotheses for the fixed effects are based on Wald type tests and the estimated variance-covariance matrix.

Multiple Imputation (MI) and MCMC Method

The multiple imputation assume that the missing data are missing at random (MAR), that is, the probability that an observation is missing may depend on the observed values but not the missing values. It also assumes that the parameters q of the data model and the parameters f of the missing data indicators are distinct. That is, knowing the values of q does not provide any additional information about f , and vice versa. If both MAR and the distinctness assumptions are satisfied, the missing data mechanism is said to be ignorable. The MI procedure provides three methods for imputing missing values and the method of choice depends on the type of missing data pattern. For monotone missing data patterns, either a parametric regression method that assumes multivariate normality or a nonparametric method that uses propensity scores is appropriate. For an arbitrary missing data pattern, a Markov chain Monte Carlo (MCMC) method that assumes multivariate normality can be used.

In MCMC, one constructs a Markov chain long enough for the distribution of the elements to stabilize to a common, stationary distribution. By repeatedly simulating steps of the chain, it simulates draws from the distribution of interest.

In Bayesian inference, information about unknown parameters is expressed in the form of a posterior distribution. MCMC has been applied as a method for exploring posterior distributions in Bayesian inference. That is, through MCMC, one can simulate the entire joint distribution of the unknown quantities and obtain simulation-based estimates of posterior parameters that are of interest.

Assuming that the data are from a multivariate normal distribution, data augmentation is applied to Bayesian inference with missing data by repeating a series of imputation and posterior steps. These two steps are iterated long enough for the results to be reliable for a multiply imputed data set ([Schafer 1997](#)). The goal is to have the iterations converge to their stationary distribution and then to simulate an approximately independent draw of the missing values.

Sample SAS code for MI using MCMC method will be provided as instruction to TFLs.

Further, as a sensitivity analysis, the pattern-mixture model approach is used to model the distribution of a response as the mixture of a distribution of the observed responses and a

distribution of the missing responses, for which the missing values can be imputed under a plausible scenario for which the missing data are missing not at random. The control-based pattern imputation, in which, the set of observations from control group are used to derive the imputation model.

Van Elteren Test for Continuous Response Variable with Strata

When assumption of normality in analysis of covariance model is violated, then a Van Elteren's test for stratified continuous data can be used. Van Elteren's test is a nonparametric test that compares treatments in the presence of blocking. The test is an extension of Wilcoxon's rank-sum test ([Van Elteren 1960](#)).

Van Elteren proposed to combine stratum-specific Wilcoxon rank-sum statistics with weights inversely proportional to stratum size.

Suppose that the data obtained for the subjects in two treatment groups are split into J strata. Then, the stratified Wilcoxon test statistic is

$$W^* = \frac{\sum_{j=1}^J a_j (T_j - E(T_j))}{\sqrt{\sum_{j=1}^J a_j^2 \text{Var}(T_j)}}$$

where $j=1, \dots, J$ denote the strata, $(T_j - E(T_j))$ and $\sqrt{\text{Var}(T_j)}$ are the numerator and denominator respectively of the Wilcoxon statistic for the data in strata j and a_j is the weight applied to each strata. The test statistic can be rewritten in the form

$$W^* = \frac{\sum_{j=1}^J a_j \sqrt{\frac{n_{0j}n_{1j}}{n_{0j} + n_{1j}}} \left(\frac{1}{n_{0j}} \sum_{k=1}^{n_{0j}} R_{0jk} - \frac{1}{n_{1j}} \sum_{k=1}^{n_{1j}} R_{1jk} \right)}{\sqrt{\sum_{j=1}^J a_j^2 \frac{1}{n_{0j} + n_{1j} - 1} \sum_{i=0}^1 \sum_{k=1}^{n_{ij}} (R_{ijk} - \bar{R}_{\bullet j})^2}}$$

where R_{ijk} is the rank of the observation X_{ijk} within strata j , $i=0,1$ denotes the treatment group, $j=1, \dots, J$ denotes the strata, $k=1, \dots, n_{ij}$ denotes the subjects within the i^{th} treatment group in the j^{th} strata and $\bar{R}_{\bullet j}$ is the average rank of all observations in strata j . This form of the test statistic was programmed into the SAS macro used for analyses.

Assuming no ties within the data, the simplified form of the variance, that is

$$\left[\sum_{j=1}^J a_j^2 \frac{1}{12} \cdot n_{0j}n_{1j} (n_{0j} + n_{1j} + 1) \right]$$

can be used.

Two weights have been used to combine results over strata:

$$\text{“Locally best”}: a_j = \sqrt{\frac{n_{0j}n_{1j}}{n_{0j} + n_{1j}}} \cdot \frac{1}{n_{0j} + n_{1j} + 1}$$

$$\text{“Type II” (used for pooled analyses)}: a_j = \sqrt{\frac{n_{0j}n_{1j}}{n_{0j} + n_{1j}}}$$

For large sample sizes (within each strata) the test statistic has a standard normal distribution; therefore the two-sided test would reject the null hypothesis if $|W^*| > u_{\alpha/2}$.

The test can easily be implemented using the SAS, PROC FREQ. The FREQ procedure is used with the TABLE statement options CMH2 and SCORES=MODRIDIT. The second CMH statistic, labeled "Row Mean Scores Differ" is the asymptotic test statistic.

As shown by [Koch et al 1982](#), the Van Elteren test is a member of a general family of Mantel-Haenszel mean score tests. For more information about the Van Elteren test and related testing procedure, refer to [Lehmann 1975](#), [Koch et al 1990](#).

